13.7.4 Visual Analogue Scale (VAS-Target Behavior)

1. INTRODUCTION

The purpose of this statistical analysis plan (SAP) is to describe the procedures and the statistical methods that will be used to analyze and report results for Protocol 1042-0900 (Amendment 8.1, August 28, 2017).

1.1 STUDY OBJECTIVES

1.1.1 Primary Objective

To evaluate the efficacy of open-label GNX as adjunctive therapy for uncontrolled seizures in children with Protocadherin 19 (PCDH19) Female Pediatric Epilepsy, Cyclin-Dependent Kinase Like 5 (CDKL5) Disorder, Dravet Syndrome, and other epileptic syndromes such as Lennox-Gastaut Syndrome (LGS) and Continuous Spike Wave in Sleep (CSWS) in an open-label proof-of-concept study.

1.1.2 Secondary Objectives

To evaluate the safety and tolerability of open-label GNX as adjunctive therapy for uncontrolled seizures in children with PCDH19 Female Pediatric Epilepsy, CDKL5 Disorder, Dravet Syndrome, and other epileptic syndromes such as LGS and CSWS in an open-label proof-of-concept study.

1.2 STUDY ENDPOINTS

1.2.1 Primary Efficacy Endpoint

The primary efficacy endpoint is the percent change in total seizure frequency (sum of individual seizures and clusters) per 28 days relative to baseline (clusters counted once regardless of the number of seizures within them).

1.2.2 Secondary Efficacy Endpoints

Secondary efficacy endpoints include:

1. Percent change in individual seizure frequency per 28-day period from baseline
2. Percent change in cluster frequency per 28-day period from baseline
3. Percent change in the average number of seizures per cluster from baseline
4. Percent change in total seizure frequency (individual seizures and clusters) per 28-day period from baseline per seizure subtype
5. Change in the percentage of individual seizure and cluster free days from baseline
6. Change in the percentage of individual seizure free days from baseline
7. Change in the percentage of cluster free days from baseline
8. Change in the longest period of time individual seizure and cluster free (% relative to number of days with seizure data) from baseline
9. Proportion of subjects with $\geq 25\%$, 50% , or 75% reduction in 28-day total seizure frequency (sum of individual seizures and clusters) compared with baseline

10. The Clinical Global Impression of Improvement: Clinician (CGII-C)
11. Clinical Global Impression of Improvement: Patient/Caregiver (CGII-P)

1.2.3 Safety Endpoints

Safety endpoints include:

- Adverse events (AEs)
- Clinical laboratory tests
- Vital signs including temperature, blood pressure, pulse rate, and weight
- Neurological and physical examinations
- 12-lead Electrocardiogram (ECG)
- Columbia-Suicide Severity Rating Scale (C-SSRS)
- Electroencephalogram (EEG)

1.2.4 Other Endpoints

Other endpoints include: Visual Analog Scale of Targeted Behaviors, Serum levels of GNX, concomitant antiepileptic drug (AED) medications, allopregnanolone, and related endogenous central nervous system (CNS) active steroids (analysis methods for the serum levels are not included in this SAP). The serum level analyses will not be in the CSR, but in a separate report.

1.3 SUMMARY OF THE STUDY DESIGN

1.3.1 General Study Design and Plan

The purpose of this proof-of-concept study is to evaluate GNX as adjunctive therapy for uncontrolled seizures in female children with PCDH19 mutations, CDKL5 mutation and SCN1A mutation (Dravet syndrome), and other epileptic syndromes such as LGS and CSWS in an open-label proof-of-concept study. After establishing baseline seizure frequency, qualifying subjects entered the main portion of the study and were treated with open-label GNX oral suspension or GNX capsules at doses up to a maximum of 1800 mg/day (63 mg/kg/day for those dosed on a mg/kg basis) for up to 6 months. Maximum study participation will be 94 weeks: a screening period to establish baseline seizure frequency, up to 26 weeks treatment, and a 52-week open-label extension (OLE) for patients who benefit from GNX treatment and up to 4 weeks down-titration. Patients who continue to benefit from GNX treatment during the 52-week OLE will be permitted to continue to receive GNX.

Approximately 10 subjects with PCDH19, 10 subjects with CDKL5 Disorder, 10 subjects with Dravet Syndrome, and up to 10 subjects with LGS, and up to 10 subjects with CSWS, were originally planned to participate. But, no subjects with Dravet Syndrome were recruited for enrollment and only 2 subjects with CSWS actually participated.

After signing the informed consent form, subjects or their legally authorized representatives were asked to chart seizures in a subject seizure calendar in order to establish baseline frequency for up to 12 weeks. After establishing baseline seizure frequency, eligible subjects entered the study and were treated with open-label GNX oral suspension or GNX capsules.

The Schedule of Events for 26-week treatment period is presented in [Table 1](#). The Schedule of Version: 2.0

Table 2.

Table 1: Schedule of Events – 26 Week Treatment Period

Week		0	2	4	8	17	26	
Visit	V1 Screening	V2 Baseline	V3 ± 3 days	V4 ± 3 days	V5 ± 3 days	V6 ± 7 days	V7 Final Visit ⁴ ± 7 days	Unscheduled Visit or Dose Escalation Visit ⁶
Screening & Diagnosis								
Informed consent	X							
Demographics	X							
Medical History	X	X						
Retrospective Seizure Diary Collection and Review	X							
Inclusion/Exclusion criteria	X	X						
Background AEDs Review	X	X	X	X	X	X	X	X
Concomitant Med Review	X	X	X	X	X	X	X	X
Safety Assessments								
ECG	X			X				
Vital Signs ⁵	X	X	X	X	X	X	X	X
Physical Examination ¹	X	X	X	X	X	X	X	X
Neurological Examination ¹	X	X	X	X	X	X	X	X
Safety Labs (Blood ⁷ and Urine ²)		X			X		X	X
Urine Pregnancy Test (WCBP)		X		X	X	X	X	
Administer C-SSRS		X	X	X	X	X	X	X
EEG		X ⁹		X ⁹	X	X	X ⁹	
Review safety and record AEs			X	X	X	X	X	X
Efficacy Assessments								
Instruct/ Provide Seizure Calendar	X	X	X	X	X	X	X	X
Subject Calendar Review	X	X	X	X	X	X	X	X
Complete CGII-C				X	X	X	X	
Instruct and Collect CGII-P				X	X	X	X	
Other Assessments								

Week	0	2	4	8	17	26		
Visit	V1 Screening	V2 Baseline	V3 ± 3 days	V4 ± 3 days	V5 ± 3 days	V6 ± 7 days	V7 Final Visit ⁴ ± 7 days	Unscheduled Visit or Dose Escalation Visit ⁶
VAS		X			X		X	
PK/PD Assessments								
Concomitant AED medications		X			X		X	
Study Drug Blood Samples					X		X	
Neurosteroid levels		X			X		X	
Study Medication								
Dispense Medication	X	X ³	X ³					
Collect bottles from prior visit study medication		X	X	X	X	X	X	X
Instruct on Down-titration							X ⁸	

AEs = adverse events; AED = antiepileptic drug; CGII-C = Clinical Global Impression of Improvement-Clinician; CGII-P = Clinical Global Impression of Improvement-Parent/Guardian; C-SSR = Columbia Suicide Severity Rating; ECG = electrocardiogram; EEG = Electroencephalography; VAS = Visual Analogue Scale; WBCP=women of childbearing potential

- 1 Physical and neurological exam records performed at the same center within 60 days of screening visit may be used in place of screening exam. Visits 3, 4, 5 and 6 may be follow-up exams. Tanner Scores will be collected.
- 2 Obtain urine sample for those who are toilet trained.
- 3 Adjust dose if necessary.
- 4 This visit could also be an Early Termination visit. The subject should be instructed on down-titration and should be scheduled for the Follow-up Visit (V11) when down-titration has been completed. At this visit, investigator confirms if the subject qualifies for the 52-week extension, subjects must have completed all scheduled clinical study visits and have shown a minimum 35% improvement in mean seizure frequency per 28 days vs. baseline.
- 5 Vital signs including temperature, blood pressure, pulse, and weight. Height will be measured at Visit 1 (Screening) only.
- 6 A dose escalation visit is required 4 to 6 days after escalation to any dose level above 54 mg/kg/day or above 1500 mg/day. A regularly scheduled visit may serve as a dose escalation visit. An unscheduled visit can occur at any time during the 26 week open-label treatment period or the 52-week extension. Samples for concomitant AEDs and study drug levels may also be drawn if warranted in the opinion of the investigator.
- 7 Safety labs can be collected at any visit if warranted in the opinion of the investigator.
- 8 If this is the last study visit, the subject should be instructed on down-titration and scheduled for Visit 11 which is the follow-up visit.
- 9 CSWS subjects: a 24-hour ambulatory or continuous EEG recorded at an epilepsy monitoring unit will be collected at Visits 1, 4 and 7. Routine/standard EEG collected at remaining visits.

Table 2: Schedule of Events – 52 Week Open-Label Extension

Week	44	62	78	
Visit	V8 ± 14 days	V9 ± 14 days	V10⁶ ± 14 days	V11⁷ Follow-up ± 7 days
AEDs Review	X	X	X	X
Concomitant Med Review	X	X	X	X
Safety Assessments				
Vital Signs ¹	X	X	X	X
Physical Examination ²	X	X	X	
Neurological Examination	X	X	X	
Safety Labs (Blood ³ and Urine ⁴)	X	X	X	
Urine Pregnancy Test (WCBP)	X	X	X	
Administer C-SSRS	X	X	X	X
EEG	X	X	X	
Review safety and record AEs	X	X	X	X
Efficacy Assessments				
Instruct/ Provide Seizure Calendar	X	X	X	
Subject Calendar Review	X	X	X	X
Complete CGI-I-C	X	X	X	
Instruct and Collect CGI-I-P	X	X	X	
Other Assessments				
VAS		X	X	
PK/PD Assessments				
Concomitant AED medications	X	X	X	
Study Drug Blood Samples	X	X	X	
Neurosteroid levels	X	X	X	
Study Medication				
Dispense Medication	X ⁵	X ⁵	X ⁵	
Collect bottles from prior visit study medication	X	X	X	X
Instruct on Down-titration			X ⁶	

Week	44	62	78	
Visit	V8 ± 14 days	V9 ± 14 days	V10 ⁶ ± 14 days	V11 ⁷ Follow-up ± 7 days

AEs = adverse events; AED = antiepileptic drug; CGI-I-C = Clinical Global Impression of Improvement-Clinician; CGI-I-P = Clinical Global Impression of Improvement-Parent/Guardian; C-SSR = Columbia Suicide Severity Rating; EEG = Electroencephalography; VAS = Visual Analogue Scale; WCBP=women of childbearing potential

- 1 Vital signs including temperature, blood pressure, pulse, and weight.
- 2 Visits 8 and 9 may be follow up exams. Tanner Scores will be collected.
- 3 Safety labs can be collected at any visit if warranted in the opinion of the investigator.
- 4 Obtain urine sample for those who are toilet trained.
- 5 Adjust dose if necessary.
- 6 If this is the last study visit, the subject should be instructed on down-titration and schedule for the Follow-up Visit (V11) when down titration has been completed.
- 7 Not applicable for subjects who continue GNX dosing after completing the 52 week OLE.

1.3.2 Randomization and Blinding

This is an open-label, uncontrolled, proof of concept study. No randomization was planned.

1.3.3 Sample Size and Statistical Power Considerations

Up to 10 subjects were planned for enrollment in this open-label, uncontrolled, proof of concept study for each patient cohort.

2. STATISTICAL METHODS

2.1 GENERAL CONSIDERATIONS

The initial clinical study report will analyze only the main portion of the study, the 26-week open-label period. The 52-week OLE portion will be analyzed and reported separately, as will the extension to the OLE portion. Separate tables and data listings will be prepared for each portion of the study. Except where noted, the tables and listings will include only events occurring within the respective periods; however demographic, background and baseline events will be included for all the periods.

In general, continuous variables will be summarized by number of subjects, mean, standard deviation (SD), median, minimum, and maximum values. Categorical variables will be summarized by counts and percentage of subjects in each category.

Summary tables will present data within cohort, alphabetically, and overall if appropriate. Source data for the summary tables and statistical analyses will be presented as subject data listings, which include data collected on the electronic case report forms (eCRFs) as well as any derived efficacy variables for all enrolled subjects.

After the informed consent is signed, baseline seizure activity will be determined by the recordings in the subject's daily seizure calendars for a period up to 12 weeks prior to the first day of treatment. Post-baseline seizure activity will be determined by the days following the first day after the first treatment. (Since times of seizures were not recorded, determinations of whether seizures on the first day of treatment preceded or followed the treatment cannot be made.)

Baselines for the VAS and safety assessments are defined as the last non-missing value of the assessment before the first dose of treatment.

The study day for all assessments that are performed on or after the first day of treatment will be calculated as:

Study Day = date of the assessment – date of first treatment + 1.

For assessments performed before the first day of treatment, the study day calculation is:

Study day = date of the assessment – date of first treatment.

2.1.1 Reporting Precision

Summary statistics will be presented to the following degree of precision, unless otherwise specified:

Statistics	Degree of Precision
Mean, Geometric mean, Median, Quartiles, Confidence limit boundaries	One decimal place more than the raw data.
Standard deviation, Standard error	Two decimal places more than the raw data.
Minimum, Maximum	The same as the raw data.
p-value	Rounded to 4 decimal places and therefore presented as 0.xxxx; p-values smaller than 0.0001 as '<0.0001'; p-values greater than 0.9999 as '>0.9999'.
Percentage	One decimal place. A percentage of 100% will be reported as 100%. Percentages of zero will be reported as 0.

For weight and height, one decimal place will be used for summary statistics. Fractional numeric values will be presented with a zero to the left of the decimal point (for example, 0.12 – 0.30).

2.2 DEFINITIONS OF ANALYSIS POPULATIONS (ANALYSIS SETS)

2.2.1 Safety Population

The safety population includes all subjects who entered into the study and received at least 1 dose of study drug.

2.2.2 Modified Intention-To-Treat Population (MITT)

The MITT population includes all subjects who entered into the study and received at least 1 dose of study drug and provided at least 1 day of post-baseline seizure calendar data. This is the primary population for the efficacy analyses.

2.2.3 Per-Protocol Population (PP)

The PP population includes all subjects who received study drug for at least 6 weeks without major protocol violations. The PP population includes all subjects in the MITT population and without major protocol violations.

2.3 TIME WINDOWS FOR ANALYSIS

For by visit safety or efficacy summaries, only scheduled visits will be analyzed.

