In Study 1042-0600 and in the ganaxolone development program overall, no clinically significant trends in changes from baseline electrocardiogram (ECG) recordings, vital signs, or physical or neurological examinations have been noted in the clinical studies, and no mean changes from baseline in clinical labs have been identified. Transient increases in LFTs (>3xULN) have been noted in less than 1% of subjects treated with ganaxolone. Serious adverse events (SAEs) reported in the ganaxolone epilepsy trials were considered by a Scientific Advisory Board to be usual for the population without any pattern attributable to ganaxolone (References 13-16 and Marinus, data on file).

Preclinical safety pharmacology and toxicology testing with ganaxolone has not revealed any end organ toxicity nor potential for ganaxolone to cause cellular mutations or carcinogenicity in studies to date. In reproductive toxicology testing, ganaxolone did not cause any malformations of the embryo or fetus in rats or mice and did not significantly affect the development of offspring. Ganaxolone is primarily metabolized by the CYP3A family of liver enzymes, but interactions based on hepatic metabolism are limited to those caused by induction or inhibition of CYP3A4/5 by other drugs such as ketoconazole.

As studies have demonstrated ganaxolone has anticonvulsant efficacy with an acceptable safety and tolerability profile in the dose range of 900-1800 mg in adults and children, the present study is planned to investigate whether ganaxolone provides anticonvulsant efficacy for female children with uncontrolled seizures and PCDH19 mutation.

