9.4.4 Study Dosing and Dosage Adjustments For subjects >30 kg

After Sponsor and Principal Investigator have reviewed subject's history, baseline seizure data and inclusion/exclusion criteria and determined a subject to be eligible for the study, ganaxolone treatment will be initiated at a dose of 900 mg/day in divided doses. The dose will be increased by approximately 20 to 50% (e.g., an increase from 900 mg/day to 1200 mg/day is a 33% increase) at intervals of not less than 3 days and not more than 2 weeks provided current dose is reasonably tolerated, until desired efficacy is achieved or a maximally tolerated dose (MTD) level is reached. Subsequent dose adjustments should

be made in increments of approximately 20 to 50% with a minimum of three days between dose changes, unless required for safety. Any and each dose escalation above 1500 mg/day requires a clinic visit scheduled 4-6 days after the dose increase to assess safety and tolerability. The maximum allowable dose is 1800 mg/day.

For subjects ≤30 kg

For children weighing 30 kg (66 lbs) or less, dosing should start at 18 mg/kg/day and be increased in ~20-50% increments at intervals of not less than 3 days and not more than 2 weeks provided current dose is reasonably tolerated, until desired efficacy is achieved or a maximally tolerated dose (MTD) level is reached. Subsequent dose adjustments should be made in increments of ~20-50% with a minimum of three days between dose changes, unless required for safety. Any and each dose escalation above 54 mg/kg/day requires a clinic visit scheduled 4-6 days after the dose increase to assess safety and tolerability. The maximum allowable dose is 63 mg/kg/day. (see Appendix 4 for suggested dose escalation schedule.)

DOWN TITRATION

At the conclusion of the study, or upon discontinuation if the subject is terminated from the study prior to Week 26, a period of down-titration from 1 to 4 weeks should be initiated. The down-titration duration will be determined by the site investigator with input from the Sponsor based on subject's age, weight, dose and duration on study medication.

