9.5.5.12 Dose Escalation Visit and Unscheduled Visits

- Review background AEDs and other concomitant medications
- Collect and review seizure calendars; provide new calendars
- Administer Columbia Suicide Scale assessed for children 7 years and older
- Perform follow-up physical and neurological examinations
- Assess for adverse events
- Measure vital signs
- Draw blood sample for hematology, chemistry; obtain urine sample from subjects who are toilet trained for urinalysis and pregnancy test for WCBP.
- Collect bottles from prior visit study medication
- Adjust dose if necessary
- Dispense study medication

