7. SAFETY ANALYSIS

All safety analyses will be performed by cohort and overall in the Safety Population. The highest percentage of the maximum allowable daily dose that subjects received will be summarized with descriptive statistics. The cumulative dosage that subjects received will be summarized with descriptive statistics, separately for subjects receiving their dosage on a mg/kg basis and those receiving it on a mg basis. For subjects who received dosing on a mg/kg basis at the start of the study and then switched to a mg basis, the doses with a mg basis will be converted to a mg/kg basis by dividing the mg by the subjects' most recent weight prior to the mg basis. A subject data listing will be provided with full details of the study drug dispensation.

Safety assessments include:

- AEs
- Clinical laboratory tests
- Vital signs including temperature, blood pressure, pulse rate, and weight
- Neurological and physical examinations
- 12-lead ECG
- EEG
- C-SSRS

Baseline is defined as the last non-missing value obtained before the first treatment. Assessments performed at multiple post-baseline time points will be summarized at each time point for which they are scheduled. The listings will include any assessments performed at unscheduled time points.

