7.2 CLINICAL LABORATORY PARAMETERS

Laboratory assessments include hematology, clinical chemistry, and urinalysis:

- Clinical Chemistry: Total Bilirubin, Aspartate Aminotransferase (AST), Alanine Aminotransferase (ALT), Blood Urea Nitrogen (BUN), Glucose, Potassium, Sodium, Calcium, Alkaline Phosphatase, Chloride, Creatinine, Carbon Dioxide (CO₂).
- Hematology: Hemoglobin, Hematocrit, Erythrocytes, Leukocytes + differential, Thrombocytes (platelet count).
- Urinalysis: pH, Color, Transparency, Specific Gravity, Urobilinogen, Ketones, Protein, Glucose

All laboratory parameters will be presented in SI units. Quantitative results (including actual value and change from baseline) will be summarized using descriptive statistics by baseline and

post-baseline visit for each laboratory test group above. Laboratory test results were evaluated as normal, abnormal (not clinically significant) or abnormal (clinically significant). The number and percentage of subjects of each category will be summarized by baseline and post-baseline time point for each parameter.

All laboratory data will be included in the listings. A pregnancy listing will be provided separately.

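### By-visit safety tables leave labs and vital signs from stand-alone dose-escalation and unscheduled visits to listings, and no table gives worst values or ULN-multiple counts

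*SAP*

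**What the plan says.** SAP 2.3 (Time Windows for Analysis): "For by visit safety or efficacy summaries, only scheduled visits will be analyzed".

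SAP 7 (Safety Analysis) repeats the rule, "Assessments performed at multiple post-baseline time points will be summarized at each time point for which they are scheduled", and says where the rest goes: "The listings will include any assessments performed at unscheduled time points".

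SAP 7.2 tabulates laboratory values and changes from baseline by visit. It also counts subjects by time point in three categories: normal, abnormal but not clinically significant, and abnormal and clinically significant. SAP 7.3.1 does the same for vital signs with low/normal/high counts, and counts weight changes of 7% or more, again by time point. SAP 2.1 includes the minimum and maximum among the descriptive statistics.

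The high-dose visit is in SAP Table 1, footnote 6: "A dose escalation visit is required 4 to 6 days after escalation to any dose level above 54 mg/kg/day or above 1500 mg/day". The same footnote lets a regularly scheduled visit serve as this visit. Protocol 9.5.5.12 gives its content: "Draw blood sample for hematology, chemistry; obtain urine sample", together with vital signs and examinations. SAP Table 1 also marks safety labs and vital signs in the combined column for unscheduled and dose-escalation visits.

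On the liver, the protocol introduction says: "Transient increases in LFTs (>3xULN) have been noted in less than 1% of subjects treated with ganaxolone". Protocol 9.3.3 excludes children with ALT or AST above 3x ULN or total bilirubin above 1.5x ULN at baseline.

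**The concern.** The dose-escalation visit exists to look at safety just after a child reaches the top of the dose range. Unscheduled and repeat tests are often done because something looked abnormal. Under SAP 2.3 and 7, results from these visits are kept out of the laboratory and vital-sign tables unless the visit coincides with one at which that assessment is scheduled.

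The one hepatic finding that the protocol names is transient and is expressed as a multiple of the ULN. By-visit statistics and investigator categories suit that kind of event poorly. They show neither each child's worst value nor how many children passed 3x ULN. Safety and tolerability is the trial's secondary objective, and SAP 9 carries the same tables into the OLE, so the gap would carry over too.

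**Working it through.** The plan states no figure to reproduce. The check compares the timing of the high-dose visits with the scheduled lab windows, follows each type of result to its table, and then sizes the issue. Days count from the first dose as day 0.

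**1. Scheduled on-treatment labs, 26-week period (SAP Table 1).** V5: 8 × 7 ± 3 = days 53 to 59. V7: 26 × 7 ± 7 = days 175 to 189. V3 (days 11 to 17), V4 (days 25 to 31) and V6 (days 112 to 126) have vital signs but no safety labs.

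**2. First required high-dose visit under uninterrupted up-titration.** Protocol 9.4.4 gives steps of about 20 to 50% at intervals of 3 to 14 days. The visit follows 4 to 6 days after the step.
- mg basis, fastest: 900 → 1350 → 1800 mg/day takes 2 × 3 = 6 days; earliest visit 6 + 4 = day 10.
- mg basis, slowest: 900 → 1080 → 1296 → 1555 mg/day takes 3 × 14 = 42 days; latest visit 42 + 6 = day 48.
- mg/kg basis, suggested schedule (Appendix 4): the first step above 54 mg/kg/day is step 6, after five intervals, so 15 to 70 days; visit at days 19 to 76.
- mg/kg basis, percentage rule alone: 18 × 1.5³ = 60.8 after 9 days. At the slow end, 18 × 1.2⁶ = 53.7 is still below 54, so a seventh step is needed, at 98 days. Visit at days 13 to 104.

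On the mg basis, every such visit falls before the V5 lab window opens on day 53. On the mg/kg basis, only some can coincide with V5. Steps taken later, after a pause in titration, are possible and are not covered by these ranges.

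**3. Where each result goes.**

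| Result | Lab or vital-sign table | Elsewhere |
|---|---|---|
| Labs at V5 or V7 (V8 to V10 in the OLE) | Yes: maximum and category counts, with no ULN multiple | Listing |
| Labs when V3, V4 or V6 doubles as the escalation visit | No: labs not scheduled there | Listing; TEAE tables if reported as an AE |
| Vital signs when a scheduled visit doubles as the escalation visit | Yes | Listing |
| Labs or vital signs at a stand-alone escalation or unscheduled visit, including repeats | No | Listing; TEAE tables if reported as an AE |
| Worst post-baseline value; ALT/AST >3x ULN; bilirubin >1.5x ULN | No table | None |

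The AE route follows from Protocol 10.5.1, where a clinically significant abnormal laboratory finding can be an AE, and SAP 7.1, where TEAEs are defined by start or worsening date and not by visit. Protocol 9.5.3 has both original and replicate results recorded, but the SAP gives no rule for using replicates.

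**4. Size.** SAP 1.3.1 reports no Dravet subjects and 2 CSWS subjects. Assuming 10 in each of the other three cohorts, n = 3 × 10 + 2 = 32. The protocol's rate is below 1%; I take 0.25% to 1% as the range and assume that it applies to this trial's follow-up.
- Expected cases: 32 × 0.0025 = 0.08 to 32 × 0.01 = 0.32.
- P(at least one) = 1 − (1 − p)³²: 7.7% to 27.5%.
- For n = 40 the range is 9.5% to 33.1%; for n = 50, 11.8% to 39.5%.

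These figures concern any >3x ULN case. Cases seen only at a non-scheduled visit are a subset, and the documents give no basis for estimating its share.

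**The case against.** A fair defence of the plan has five parts.

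- **The loss is partial.** A reader might infer that no >3x ULN rise could reach any summary table. The documents do not support that: there is the maximum at scheduled lab visits, the abnormal categories and the AE route. V7 may also serve as the early termination visit, so a child withdrawn with a rise may have a tabulated draw. This stands. None of these routes counts children above 3x ULN, however, and the AE route depends on investigator judgment and does not show the size of the rise.
- **The escalation visit may count as scheduled.** Protocol 9.4.4 says "Any and each dose escalation above 1500 mg/day requires a clinic visit scheduled 4-6 days after the dose increase to assess safety and tolerability". The SAP schedule puts it in the unscheduled column. This is a real ambiguity, and the SAP should settle it. Even if the visit counts as scheduled, the SAP defines no analysis time point for it.
- **Listings are enough for so few children.** All results are listed, and about 32 children can be read case by case. Protocol 9.7.6 also promises flags in listings for critically significant laboratory, ECG and vital-sign changes. SAP 7.3.1 and 7.3.3 keep flags for vital signs and ECG, but SAP 7.2 mentions none for labs. The protocol reviewed dates from April 2016 and the SAP cites Amendment 8.1 of August 2017, so the laboratory flag may have changed between the two. The argument lowers the priority of the point but does not remove it.
- **The ULN multiples are not analysis thresholds.** True: they are eligibility limits and a background statement. They are still the terms in which the protocol describes the liver finding, and the SAP already counts a threshold for weight.
- **Other blood draws may exist.** The protocol synopsis and 9.5.4 name a 2-week draw, but the V3 procedures and both schedule tables omit it. As the SAP stands, it is not a scheduled lab point.

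A reader might also size the gap by how often two scheduled draws would meet a rise of d weeks (d up to 8) with onset uniform over 26 weeks: 2d/26, or 15%, 31% and 62% for 2, 4 and 8 weeks. That describes the sampling schedule. Many of the remaining rises would be seen at no draw at all, and no table could recover them. Uniform onset also fits poorly with a concern about the days after a dose increase.

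**Conclusion.** The point holds in a limited form, with certainty as to the rules and little as to size. The omission of stand-alone escalation and unscheduled results from the laboratory and vital-sign tables follows directly from SAP 2.3, 7, 7.2 and 7.3.1, on the reading that the escalation visit is not a scheduled time point. For a rise to be missing from every laboratory summary table, it must be recorded at a non-scheduled draw and be absent at each scheduled one. To be missing from all summary tables, it must also not be reported as an AE. Such cases are expected to be few. For vital signs the gap is one of completeness; the documents show no specific vital-sign signal that would be lost.

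No efficacy result is affected. The change is a worthwhile, inexpensive improvement to how the secondary objective is reported. The timing result assumes uninterrupted titration under Protocol 9.4.4. The sizing rests on the assumed enrolment and rate.

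**What to change.** 1. SAP 2.3: keep the by-visit tables on scheduled visits. State how dose-escalation visits are classed, including when a regular visit doubles as one, and how repeat results are handled.
2. SAP 7.2: add an any-post-baseline summary, by cohort and overall, using every assessment, including dose-escalation, unscheduled and repeat ones. Give the worst value per subject, the baseline-to-worst shift, and the number (%) with ALT or AST >3x ULN and with total bilirubin >1.5x ULN.
3. SAP 7.3.1: add the matching worst-value and shift summary for vital signs.
4. SAP 9: produce the same tables for the OLE.
5. Show the number of assessments per subject beside these counts.

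Cost: SAP wording and a few extra tables from data already collected. The downside is that worst-value counts rise with the number of tests a child has, so children with more escalation or unscheduled visits have more chances to be counted. Item 5 lets the reader allow for that.
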